### **Analysis of the Secondary Efficacy Endpoint(s)**

Glycemic variability indicators will be obtained from CGM downloads for the 14 days prior to a follow-up data collection time point. As guided by published standardized CGM metrics, data will be transformed to identify number of measurements and percent TIR, time below range (<70 mg/dL) (TBR), and time above range ( $\geq 180$  mg/dL) (TAR), mean sensor glucose, and coefficient of variation (CV) of glucose values during each 14-day period. We also will track the percent CGM wear time.

CGM data will be analyzed using library GLU in R. using mixed effect models. These models will quantify the impact of our intervention on glucose control over time. The independent variables will be baseline time in range, child age, and a random subject effect to account for correlation of measurements on the same subject. Interaction terms of age and baseline time in range with the intervention will explore possible effect modification ( $p < 0.10$ ) of these characteristics. We will also explore differences between time points and average outcome by parent education level and income. Results will be reported as least-squares means (LSMEANS) with standard errors. Casewise deletion will be used to handle missing data.

A battery of validated survey measures exploring diabetes-specific self-management skills and quality of life will be completed by the child and caretaker, including: Type 1 Diabetes and Life (T1DAL), Diabetes Self- Management Profile (DSMP), Self-Efficacy for Diabetes (SEDS), and Problem Areas in Diabetes (C-PAID). Perceived benefits and barriers to CGM use will be assessed using the CGM Benefits and Burdens scale. Surveys will be completed by a single, consistent parent/caregiver throughout the study, preferably the one most involved in medical care. We will summarize self-management skills and treatment satisfaction by different time points. Differences in participant self-management skills and patient satisfaction will be reported as mean Likert scale score and standard deviation. Similar analysis using linear longitudinal regression analysis will be conducted. Results will be reported as least-squares means (LSMEANS) with

standard errors. Casewise deletion will be used to handle missing data.

The incidence of DKA and DKA event rate per 100 person-years, incidence of severe hypoglycemia and severe hypoglycemia event rate per 100 person-years, incidence of ED visits and ED visit event rate per 100 person-years, incidence of hospital admissions and hospital admission event rate per 100 person-years, will also be compared using linear longitudinal regression analysis. Results will be reported as least-squares means (LSMEANS) with standard errors. Casewise deletion will be used to handle missing data.

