## **Section 4: Study Design**

Dyads of youth with T1D aged 8-12 years and their primary diabetes caretakers identifying as non-Hispanic Black or Latinx will be recruited to participate in a prospective cohort pilot study exploring feasibility and acceptability of SMA and the impact on glycemic control, self-management skills, and health related quality of life. This trial will employ an enrollment visit, SMA visits every 3 months over a 12-month study period, and a follow-up 6-month observational period to continue to evaluate outcomes once patients return to routine individual follow up care. The study will include a single intervention group participating in the SMA visits (n=20).

All staff participating in the SMA visit will receive comprehensive training on how to facilitate the SMA discussion sessions effectively. All topics that will be covered at each SMA visit will be reviewed by the study staff ahead of the visit. Potential participants will

be screened for participation using our electronic medical records system and will be approached during routine clinical visits. After explaining all study procedures, informed consent using an IRB-approved consent form will be obtained for all participants. After obtaining consent, a blinded Dexcom G6 CGM will be placed on the participant. Participants will be instructed to wear the blinded CGM for 10 days in order to obtain baseline glycemic control data prior to starting the SMA visit intervention. At the completion of the 10 day wear period, participants will mail back the blinded CGM in a pre-addressed envelope so that the data can be assessed within 30 days of the wear time. Because SMA visits will be used in place of routine clinic visits and because participants will not require any additional in person study visits, we anticipate significant interest in participation with minimal barriers. Secure REDCap surveys will be sent to participants via email 1 week before each follow-up visit. If the surveys have not been completed at the time of the visit the participant will be asked to complete the measures using an iPad or paper in clinic at the time of their visit. Youth who elected not to use a CGM for routine clinical care, will be asked to wear a blinded professional CGM for 10 days prior to each visit whenever possible.

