## **5.2 Inclusion Criteria**

In order to be eligible to participate in this study, an individual must meet all of the following criteria:

1. Patients clinically diagnosed with T1D managed with insulin injections for at least 1 year
2. Non-Hispanic Black or Latinx ethnicity
3. Public healthcare insurance
4. Male or female ages  $\geq 8$  and  $\leq 12$  years
5. No prior use of CGM within 60 days of enrolment
6. Poorly controlled T1D: one A1c value  $> 8\%$  in the preceding year
7. Fluent in English as the Dexcom technology is currently available only in English
8. Participation of the primary diabetes caregiver

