### **8.2 Statistical Hypotheses**

Primary Outcome: feasibility and acceptability of SMA among underserved youth with T1D.

Hypothesis 1a. Rates of SMA retention (>80%) at 12-months and satisfaction with visits (>80%) will be high.

Null Hypothesis 1a: n/a

Hypothesis 1b: Thematic analysis of semi-structured interviews will identify high satisfaction with SMA.

Null Hypothesis 1b: n/a

Secondary Outcome: preliminary impact of SMA on glycemic control, self-management skills, self-efficacy, diabetes related quality of life, and treatment satisfaction among underserved children with T1D and their caregivers

Hypothesis 2a: CGM percentage wear time and sustained use, as defined by use within the 2 weeks prior to the visit, will be greater upon completion of the SMA intervention at 12 months compared to baseline

Null Hypothesis 2a: CGM percentage wear time and sustained use, as defined by use within the 2 weeks prior to the visit, will not be significantly different upon completion of the SMA intervention at 12 months

Hypothesis 2b: CGM time in range (70-180 mg/dL) will be greater and the glucose management indicator (GMI) lower for youth upon completion of the SMA intervention group at 12 months compared to baseline.

Null Hypothesis 2b: CGM time in range (70-180 mg/dL) will not be significantly different upon completion of the SMA intervention at 12 months

Hypothesis 2c: Diabetes-specific quality of life, self-management behaviors, and self-efficacy scores will be greater upon completion of the SMA intervention at 12 months compared to baseline.

Null Hypothesis 2c: Diabetes-specific quality of life, self-management behaviors, and self-efficacy scores will not be significantly different upon completion of the SMA intervention at 12 month

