### **8.3 Analysis Datasets**

Data analysis will be conducted according to a per-protocol analysis as we will be unable to obtain appropriate data from those who withdraw from the study. Participants with incomplete data will be included in analyses when possible.

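### The CGM models condition on baseline TIR although month 12 is compared with baseline in one group, and the plan does not say how the change, its SE or a missing baseline is handled

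*Combined protocol and SAP*

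**What the plan says.** Section 8.4 (Analysis of the Secondary Efficacy Endpoint(s)) sets out the CGM model: "The independent variables will be baseline time in range, child age, and a random subject effect". It then says: "Results will be reported as least-squares means (LSMEANS) with standard errors. Casewise deletion will be used to handle missing data". The Statistical Analysis entry of the Protocol Summary and the Secondary Outcomes part of Section 6.4 list the same covariates. No visit or time term is listed, although Section 8.4 speaks of impact over time and of differences between time points. The same section plans an interaction of baseline TIR with the intervention to explore effect modification.

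Section 4 describes a single intervention group of 20. Under Hypothesis 2b (Section 8.2), TIR is to be higher and GMI lower "upon completion of the SMA intervention group at 12 months compared to baseline".

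Baseline CGM comes from one blinded wear: "Participants will be instructed to wear the blinded CGM for 10 days in order to obtain baseline glycemic control data". The sensor is then returned by post: "At the completion of the 10 day wear period, participants will mail back the blinded CGM in a pre-addressed envelope". Section 5.2 requires "No prior use of CGM within 60 days of enrolment", so no recent CGM record can stand in for it. On incomplete data, Section 8.3 says only: "Participants with incomplete data will be included in analyses when possible". Section 8.1 states that there will be no formal SAP, so Section 8.4 is the full specification.

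**The concern.** Adjusting for baseline is natural when two arms are compared at follow-up. Here there is one arm and the target is the change from baseline, so the baseline mean is itself one of the two quantities compared. A model that takes baseline as a fixed covariate evaluates the 12-month mean at the observed average baseline and treats that average as known. The SE attached to that mean leaves out the sampling error of baseline. If it is then used for the change, the interval is too short and the test rejects too often.

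The second issue is missing data. A child without a usable baseline sensor has a missing covariate on every row. Casewise deletion then removes all of that child's follow-up CGM records from the TIR, TBR, TAR, mean glucose and CV models, however complete they are.

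Section 2.4 expects the results to inform later randomized studies, so the stated precision of the TIR change will be used.

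**Working it through.** **Inputs from the protocol.** One group, n = 20 (Section 4). Month 12 against baseline (Section 8.2). Follow-up at 3, 6, 9 and 12 months, plus 15 and 18 months (Table 1). Two-sided inference (Section 8.4). The protocol gives no SD, effect size, power or correlation, so there is no stated figure to reproduce.

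**Assumptions.** Equal SD (sigma) at each visit, correlation r between visits, alpha 0.05. r is not in the documents and is shown as a range.

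**Step 1: reading A.** Only follow-up visits are responses, and baseline TIR is a covariate.
- SE of the 12-month LSMEAN at mean baseline = sigma × sqrt((1 − r²)/n)
- SE of the mean change = sigma × sqrt(2(1 − r)/n)
- Ratio = sqrt((1 − r²)/(2(1 − r))) = sqrt((1 + r)/2), below 1 for every r < 1

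The table gives the two SEs before division by sqrt(n), in units of sigma. The large-sample rejection rate is 2 × P(Z > 1.96 × ratio). The last column is a simulated analysis of covariance at n = 20 with t on 17 df (10,000 runs).

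| r | sqrt(1 − r²) | sqrt(2(1 − r)) | Ratio | SE too small by | Large-sample rejection | Simulated rejection |
|---|---|---|---|---|---|---|
| 0.4 | 0.917 | 1.095 | 0.837 | 16% | 10.1% | 9.7% |
| 0.6 | 0.800 | 0.894 | 0.894 | 11% | 8.0% | 7.6% |
| 0.8 | 0.600 | 0.632 | 0.949 | 5% | 6.3% | 6.3% |

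A random-intercept model on the 3, 6, 9 and 12-month rows, with a visit factor added (8,000 runs, n = 20, t on 17 df), gave SE ratios of 0.80, 0.87, 0.92 and 0.96 at r = 0.3, 0.5, 0.7 and 0.9. Rejection was 9.7%, 6.9%, 5.7% and 4.3%, so the inflation fades as r rises and is gone at r = 0.9.

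**Step 2: reading B.** Baseline is both a covariate and a response row, and the month-12 minus baseline contrast is reported. In the same simulations at n = 20, rejection for that contrast was 4.9% to 5.4%. The contrast is sound.

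**Step 3: baseline as a response only.** Visit is a factor with a random subject effect and no baseline covariate. At n = 20 the model SE of the contrast was 0.263, 0.223 and 0.173 sigma at r = 0.3, 0.5 and 0.7, against empirical SDs of 0.266, 0.222 and 0.173. Rejection was again 4.9% to 5.4%.

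**Step 4: a missing baseline.** In a simulated set of 20 children with four follow-ups and one missing baseline, the model with the covariate kept 19 children and 76 rows. Without the covariate it kept 20 children and 80 rows. Each such child loses 4 follow-up windows to month 12, or 6 to month 18.

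**Step 5: what those rows are worth.** With k children lacking baseline and V the compound-symmetric covariance, the information for the visit means is (20 − k) × V⁻¹ if they are dropped. If they are kept, k times the inverse of V's follow-up block is added. For r = 0.4 to 0.8 and 4 or 6 follow-ups, keeping k = 1, 2 or 3 children lowers the SE of the 12-month change by about 1%, 2% or 3%. Failure rates are not in the documents; 1 to 3 of 20 corresponds to an assumed 5% to 15%.

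**The case against.** The strongest reply is that the SE shortfall depends on two things the plan does not state: that only follow-ups are responses, and that a visit LSMEAN's SE is taken as the SE of the change. The references to impact over time and differences between time points could equally mean an explicit visit contrast, which is correct. This stands. A reader might infer that the error bars for Hypothesis 2b are too narrow whatever is done; the text leaves the point open and does not support that.

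A related reply is that the covariate is not the only cause. A per-visit LSMEAN's SE is not the SE of a change in any model. Without the covariate, its ratio to the SE of change is 1/sqrt(2(1 − r)), or 0.91, 1.12 and 1.58 at r = 0.4, 0.6 and 0.8. This also stands, so removing baseline TIR without changing what is reported would not be enough.

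A reader might also infer that a failed baseline sensor costs much information, since up to six windows per child vanish. Step 5 shows otherwise: a child with no baseline cannot show a within-child change. The loss is untidy but small, and it does not justify an added study procedure. The sentence in Section 8.3 on including incomplete data does not rescue the child, because it gives no method for a missing covariate under casewise deletion.

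Finally, Section 2.2 mentions matched routine-care patients, and Sections 4 and 6.3 mention randomization, which might suggest a comparison group for which baseline adjustment would be apt. Section 4 defines one group, the Section 8.2 hypotheses are against baseline, and the model has no group term.

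**Conclusion.** The point holds as a gap in specification with a conditional cost. The model conditions on one side of its own contrast, and the plan does not say which rows are responses or how the change and its SE are obtained. On the follow-up-only reading, with the LSMEAN's SE used for the change, the SE for TIR is 5% to 16% too small and the 5% test runs at about 6% to 10%, for assumed r of 0.8 to 0.4 at n = 20. With baseline as a response and the explicit contrast, neither figure applies.

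The exact ratio holds only for TIR. GMI, TBR, TAR, mean glucose and CV would be adjusted for baseline TIR, not for their own baseline. Removal of a child without baseline affects every CGM model under either reading, at a cost of about 1% to 3% in the SE of the 12-month change for 1 to 3 children.

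These are secondary analyses in a pilot whose primary outcome is feasibility and acceptability, so the consequence is modest. The correction is cheap and worth making because no separate SAP will settle the question.

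**What to change.** In Section 8.4, and in the matching text of Section 6.4 and the Protocol Summary:
- Drop baseline TIR from the main CGM models.
- Enter each metric's own baseline as the visit-0 response, with visit as a factor, child age and a random subject effect.
- Report the month-12 minus baseline contrast with its own SE and confidence interval, not only per-visit LSMEANS.
- State that deletion is by missing record, not by child. If whole children are deleted, one without baseline is still lost after the covariate is removed.
- Keep the planned effect-modification analysis by baseline TIR as a separate exploratory model.

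The cost is model wording and one extra exploratory model. No visit, sensor wear or data item is added.

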SMA Structure: SMAs will consist of 4-6 underserved youth with T1D and their primary diabetes caregiver. All youth and caretakers will complete standard check-in procedures with the clinic medical staff, including routine clinical intake questionnaires, vital sign assessments and point-of-care fingerstick A1c measurements. Before each session, dyads will be invited to submit questions to the research team that will then be anonymously reviewed and discussed among the group during the SMA. In the event that no questions are submitted by families, the facilitator will begin the discussion with stories and questions related to technology use and potential barriers in order to focus the discussion on the aspect of diabetes management being highlighted in that specific SMA. After discussing the questions, the facilitator will lead a group discussion focusing on the topic of the day. During each visit, the facilitator role will be shared by a pediatric endocrinologist, CDCES, nutritionist, and psychologist. Youth and caregivers will individually meet with the endocrinologist at different time points during the session to update personal management plans and goals of care. The group visit will conclude with a review of the core concepts discussed. Youth will be encouraged to set and share individual goals to be addressed before the next SMA.

Enrollment visit: This visit will occur at a routine clinic visit once a patient expresses interest in participating in the study. Alternatively, patients expressing interest in enrolling who are unable to do so at a routine clinic visit will have the option to come back for enrollment at a different time. A study team member will meet with the patient and family to review the study details and obtain consent. Randomization will be completed after consent has been obtained. A blinded Dexcom G6 pro CGM will be placed on the patient and be worn for 10 days in order to collect baseline data prior to starting the intervention. Phone applications that will allow for sharing of CGM data between patients and the diabetes clinical care team will be downloaded and established before the end of the visit.

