**Follow Up SMA:** Follow up SMA will be scheduled 3, 6, 9, and 12 months from the initial group visit. CGM data from 14 days prior to each SMA will be reviewed by the endocrinologist ahead of the group visit. Discussions and education guided by the facilitators will focus on issues that have been described in the literature as potential barriers to CGM use and adherence. Recurrent alerts and alarms can result in alarm fatigue, and falsely low glucose readings and sensor or transmitter failures have been cited as reasons for discontinuing CGM use. The continuous nature of CGM data has been shown to place significant demands on patients and their families, and to create stress related to the constant need for diabetes-related attention. Follow up visits will focus on optimized use of CGM alarms and prevention of alarm fatigue. Psychologists and CDCES will discuss strategies to cope with the on-body presence and potential embarrassment resulting from CGM wear and to optimize parent-child communication surrounding CGM. Nutritionists will highlight the impact of different foods on glycemic trends and discuss strategies to optimize control. SMA will also allow ample opportunity to jointly review de-identified CGM reports and how to effectively interpret data and make management changes in response to CGM data, empowering patients and families to improve self-management and reduce stress related to CGM use. Active participation in discussions and group exercises will continue to strengthen the community feeling and social support network within the SMA group. Any participant that chooses to discontinue CGM during the 12 month study period will wear a blinded CGM 10 days prior to the follow up visits to allow for complete data collection. Upon completion of the final SMA visit at month 12, dyads will be contacted to schedule a semi-structured interview and will then return to standard clinical care.

**3-Month and 6-Month Post-Intervention Follow-Ups:** Survey measures and assessments of glycemic control will be repeated after 3 months and 6 months of routine clinical care to assess for long-lasting effects of the intervention.

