## **8.5 Sample Size**

As this is a pilot study, we plan to enroll up to 20 parent-child dyads. We anticipate low dropout rates, but do plan to enroll new subjects to keep the total number of subjects at up to 20 in case of attrition. If there is a sufficient number of new subjects enrolled to replace those that drop out, a new SMA group will be created so that newly enrolled subjects will be able to start the intervention from the baseline visit.

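### The group visits create 4-5 clusters, but the secondary change analyses have no group term, so their SEs, CIs and p-values will be too small if members of a group change together after baseline

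*Combined protocol and SAP*

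**What the plan says.** Section 4 (SMA Structure) sets the unit of delivery: "SMAs will consist of 4-6 underserved youth with T1D and their primary diabetes caregiver". Section 8.5 sets the size: "As this is a pilot study, we plan to enroll up to 20 parent-child dyads". Section 4 describes a single arm, so every child is treated in a group. Among the aims of the follow-up sessions is to "strengthen the community feeling and social support network within the SMA group".

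In Section 8.4 (Analysis of the Secondary Efficacy Endpoints), the CGM mixed models contain baseline time in range, child age and "a random subject effect to account for correlation of measurements on the same subject". For the surveys the text says: "Similar analysis using linear longitudinal regression analysis will be conducted". The rates of DKA, severe hypoglycemia, ED visits and admissions "will also be compared using linear longitudinal regression analysis". SMA group appears in none of these models. The document mentions no cluster-robust standard error, ICC or design effect, and Section 8.1 says there will be no separate SAP.

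Inference on change is intended. Section 8.2 gives null hypotheses for change to 12 months, for example "CGM time in range (70-180 mg/dL) will not be significantly different upon completion of the SMA intervention at 12 months". Section 8.4 calls for two-tailed p-values and confidence intervals, and for least-squares means with standard errors.

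**The concern.** A random subject effect deals with repeated measurements on one child. It does nothing about correlation between children who attend the same sessions. Peer support and group discussion are part of how the SMA is meant to work, so it is plausible that members of a group improve, or fail to improve, together. The 20 changes would then carry less information than 20 independent ones, and the planned analysis would overstate its precision.

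What is at stake is how the preliminary glycemic and survey results are read. Section 2.4 expects the study to inform later randomized trials. A 12-month change reported with an interval that is too narrow would look more certain than it is.

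**Working it through.** **Inputs.** From the protocol: group size m = 4-6 (Section 4), N up to 20 (Section 8.5), two-tailed inference (Section 8.4), change from baseline to 12 months (Section 8.2). Assumed, because the protocol gives no value: ICC of change from 0 to 0.20, and a 5% level. The plan has no power or precision figure to reproduce.

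**Number of groups.** 20/4 = 5 and 20/6 = 3.3, so about 4-5 groups.

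**Which correlation matters.** A group difference that is constant over all visits, baseline included, cancels in the change. In a simulated random-subject-intercept model it left the type I error at 0.050-0.051 and the SE ratio at 1.00. Only a shared effect on change matters. The baseline blinded CGM is worn before the first SMA, so any shared effect of the sessions on CGM measures enters after baseline and is of this kind.

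**Design effect.** DE = 1 + (m - 1) × ICC; the SE is understated by √DE; effective n = 20/DE. For m = 5 and ICC 0.10: DE = 1 + 4 × 0.10 = 1.40, √1.40 = 1.18, 20/1.40 = 14.3.

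| ICC of change | DE (m = 5) | SE factor, m = 4 / 5 / 6 | Effective n (m = 5) | Type I error, 4 groups of 5 | Type I error, 5 groups of 4 |
|---|---|---|---|---|---|
| 0 | 1.00 | 1.00 / 1.00 / 1.00 | 20.0 | 5% | 5% |
| 0.01 | 1.04 | 1.01 / 1.02 / 1.02 | 19.2 | 5.5% | 5.3% |
| 0.05 | 1.20 | 1.07 / 1.10 / 1.12 | 16.7 | 7.2% | 6.6% |
| 0.10 | 1.40 | 1.14 / 1.18 / 1.22 | 14.3 | 9.7% | 8.6% |
| 0.20 | 1.80 | 1.26 / 1.34 / 1.41 | 11.1 | 14.4% | 12.2% |

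The type I errors come from simulated change scores for 20 children (200,000 runs), tested with a t-test that ignores groups. They run slightly above what √DE alone implies because the sample variance also shrinks, by the factor 1 - (m - 1) × ICC/(N - 1). At ICC 0.20 that is 1 - 0.8/19 = 0.958, and the true ratio is √(1.80/0.958) = 1.37.

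**Closer to the planned model.** A random-subject-intercept model over five visits, with 4 groups of 5 and ICC 0.01, 0.05, 0.10 and 0.20, gave type I errors of 5.4%, 7.5%, 10.4% and 17.2% for a shared post-baseline shift. For a group effect that varies by visit they were 5.4%, 7.0%, 9.2% and 13.3%.

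**Group-mean analysis.** A t-test on group mean changes held about 5% throughout. Its critical value is 3.18 (4 groups, 3 df) or 2.78 (5 groups, 4 df), against 2.09 on 19 df. With no clustering, the interval is therefore about 3.18/2.09 = 1.52 or 2.78/2.09 = 1.33 times as wide.

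**Random group term.** With 4 groups of 5, the ANOVA estimate of the group variance of change is zero or negative in 48% of runs at ICC 0.05 and 40% at ICC 0.10.

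**The case against.** The strongest reply is that no understatement has been shown. The protocol gives no ICC; at zero nothing is wrong, and at 0.01 the SE is off by 1-2%. A reader might infer from the missing term that the reported SEs are certainly too small. The documents support only the conditional statement. That part of the objection stands.

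Several features could keep the ICC low. Each dyad meets the endocrinologist individually, CGM is used at home, and missed sessions may be made up with another group. A reader might also take shared facilitators as proof of clustering, but Section 4 lists one set of roles and does not say that teams differ between groups. What remains is the peer and community mechanism, which makes correlation plausible without fixing its size.

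Scope is limited too. The quoted random effect belongs to the CGM models. Section 8.4 names no specific model for A1c, so it cannot be said that this model understates the A1c standard error. The primary outcomes are percentages set against benchmarks, with the null hypotheses given as not applicable, and they are unaffected. The secondary aim is called preliminary, and no stated decision rests on its p-values.

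Finally, the obvious remedy is weak. In nearly half of trials with a true ICC of 0.05, a random group term would be estimated at zero and the model would revert to the planned one. A group-mean test is valid but costly: for an assumed standardized change of 0.66 at ICC 0.05 with 4 groups of 5, its simulated power is about 46%, against about 78% for the test that ignores groups (which itself rejects too often under the null).

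These arguments limit the claim and shape the remedy. They do not remove the gap: the plan neither allows for between-group variation in change nor shows how sensitive its results are to it.

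**Conclusion.** The point holds in conditional form. The planned secondary change analyses will understate uncertainty if members of an SMA group change together after baseline. The effect is negligible for an ICC of change of 0-0.01 and material at 0.05-0.10, where with groups of 4-6 the SE is understated by about 7-22% and the type I error is about 7-10%. At 0.20, with 4 groups of 5, the error reaches about 14% on change scores. These figures rest on the assumed ICC range, a 5% level and roughly equal groups totalling 20 children. The matter merits a sensitivity analysis and does not threaten the primary aim.

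**What to change.** In Section 8.4:

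1. Record each child's home SMA group and analyse by it whatever make-up sessions were attended. Children in a new group formed for replacements (Section 8.5) have that group as home group.
2. Keep the planned models. Add a pre-specified sensitivity table for the 12-month change in time in range and in the survey scores, giving (a) confidence intervals inflated for an ICC of change from 0 to 0.20, and (b) a t interval on group mean changes with (groups - 1) df.
3. Label the secondary p-values exploratory.
4. Do not make random group terms the main remedy. Report any estimated group ICC only with its interval, because 4-5 groups estimate it very poorly.

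The cost is recording group assignment and one small table. The downside is wider intervals, especially for (b), so (b) should be read as a check beside the planned result.

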### **8.4 Description of Statistical Methods**

#### **General Approach**

Descriptive measures will be used to summarize participant demographic information. P-values and confidence intervals will be two-tailed. Covariates will be pre-specified. Tests to assess normality will be performed and data transformation or non-parametric analyses will be used when necessary.

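### With one group, the baseline-TIR-by-intervention term screened at p<0.10 cannot be identified as effect modification

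*Combined protocol and SAP*

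**What the plan says.** The design has one arm. Section 4 states: "The study will include a single intervention group participating in the SMA visits (n=20"). Section 8.5 treats 20 dyads as a ceiling and gives no power calculation.

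Section 8.4 (Analysis of the Secondary Efficacy Endpoint(s)) specifies mixed models for the CGM metrics: "The independent variables will be baseline time in range, child age, and a random subject effect". It then adds: "Interaction terms of age and baseline time in range with the intervention will explore possible effect modification", flagged at p<0.10. The same sentence stands in the Protocol Summary (Statistical Analysis) and in Section 6.4 (Secondary Outcomes). The General Approach makes p-values two-sided.

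The listed terms include no intervention, visit or time effect. The plan does not say how the intervention is coded in the interaction, or whether the baseline TIR value is also an outcome row. Hypothesis 2b (Section 8.2) sets the TIR contrast as "upon completion of the SMA intervention group at 12 months compared to baseline". Baseline TIR comes from a single short blinded wear (Section 4: "Participants will be instructed to wear the blinded CGM for 10 days in order to obtain baseline glycemic control data"), whereas follow-up uses 14-day windows. Section 8.6 lists no measures against bias.

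**The concern.** With no second arm, an interaction with the intervention can only be an interaction with before/after, time or period. Under before/after coding it asks whether the change in TIR depends on baseline TIR. Baseline TIR enters that change with a minus sign and carries the noise of one short recording. A child whose baseline window happened to be bad will tend to look improved later, and a child whose window happened to be good will tend to look worse, whatever the SMA does. The p<0.10 rule then tests whether the correlation between windows equals 1, not whether the intervention works differently by starting level.

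At stake is a reported finding that children with the lowest baseline TIR gain most. Section 2.4 expects the results to inform future randomised trials, so such a finding could influence their design.

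**Working it through.** The plan gives no error rate, SD or correlation for this term, so there is no figure of its own to reproduce.

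**Inputs from the documents.** One group, n up to 20; two-sided p<0.10; baseline plus visits at 3, 6, 9 and 12 months, then 15 and 18 months; random subject effect; casewise deletion. The retention benchmark of 80% gives 0.80 × 20 = 16 for a smaller case.

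**Assumptions.** Correlation rho between baseline and follow-up TIR of 0.5 to 0.95; normal data; equal SDs; no missing visits; every child has the same TIR shift, so there is no effect modification.

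**Expected slope.** With common variance s², the covariance of (Y12 − Y0) with Y0 is rho·s² − s². The slope of change on baseline is therefore −(1 − rho), and the common shift affects only the intercept. The variance of the change is 2(1 − rho)s², so the correlation of change with baseline is −√((1 − rho)/2).

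**Approximate false-flag rate, n=20.** P ≈ Φ(atanh|r|·√17 − 1.645).
- rho 0.5: r = −0.50, P ≈ 73%.
- rho 0.7: r = −√0.15 = −0.39, P ≈ 52%.
- rho 0.9: r = −√0.05 = −0.22, P ≈ 24%.

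**Simulated rate of p<0.10 with no modification** (1,000 studies per cell for mixed models, 6,000 for the change regression; nominal 10%; n=20 unless stated):

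| Model | rho 0.5 | 0.6 | 0.7 | 0.8 | 0.9 | 0.95 |
|---|---|---|---|---|---|---|
| Before/after × baseline TIR, random intercept, baseline row in outcome | 89% | 81% | 72% | 54% | 31% | 21% |
| 12-month change on baseline | 76% | 66% | 54% | 41% | 25% | 17% |
| Same, n=16 | 67% | 56% | 45% | 33% | 22% | 16% |
| Linear time × baseline TIR, baseline row in outcome | 61% | – | 42% | 32% | 18% | – |
| Post-baseline rows, time × baseline TIR | 9% | – | 9% | – | 8% | – |
| Post-baseline rows, SMA period versus months 15–18 × baseline TIR | 9% | – | 11% | – | 10% | – |

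In the before/after model the mean coefficient follows −(1 − rho): −0.497 at 0.5, −0.299 at 0.7, −0.050 at 0.95. When the change regression was repeated, nearly all false flags pointed to the lowest baseline gaining most.

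**Decaying correlation.** The table assumes constant correlation. With rho of 0.7 to 0.8 at 3 months, falling 5% to 20% per further 3 months, the before/after model flags 65–85%. The two post-baseline models flag 22–70% and 31–73%.

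**Unequal windows.** If days are independent, baseline noise variance is 14/10 = 1.4 times that of follow-up. The change regression at rho 0.7 then flags 69% instead of 54%.

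**Oldham / Pitman-Morgan check.** Correlating the change with the mean of the two values flags 9.4–10.2% at n=20. That correlation is proportional to Var(Y12) − Var(Y0), so the result depends on equal variances. Suppose individual response has variance v (in units of baseline variance) and is independent of baseline. The correlation becomes v/√((2 + 2rho + v)(2 − 2rho + v)). At rho 0.7 this is 0.5/√(3.9 × 1.1) = 0.24 for v = 0.5 and 1/√(4.4 × 1.6) = 0.38 for v = 1. The simulated flag rate is about 27% to 51%, nearly all towards higher baseline gaining more, with no modification by baseline present.

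**The case against.** The strongest reply is that the plan never says baseline is an outcome row. Baseline TIR is listed as an independent variable, and the 14-day CGM windows are tied to follow-up time points, so a model of post-baseline rows only is a fair reading. Under constant correlation its error is nominal. This stands as a limit on the size of the problem. It does not rescue the term, which on that reading no longer addresses change from baseline and is itself inflated if correlation decays.

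A reader might infer that the plan will usually report a false modifier. The documents do not support that. They give no rho, and rates above 50% need rho up to about 0.8 in the random-intercept model, 0.7 in the change regression, or 0.6 in that regression with 16 children. A reader might also infer that any modifier found would not be real. Children with low baseline TIR may truly gain more; the design simply cannot tell that apart from regression to the mean.

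The analysis is exploratory, on secondary outcomes, in a pilot whose primary outcome is feasibility and acceptability. That limits the consequence. Nothing in the protocol plans to carry the interaction into eligibility or stratification.

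A comparator might be inferred from the matched routine-care data in Section 2.2 or the mention of randomisation at the enrolment visit. Section 4 describes a single group, and Section 8 contains no comparative analysis.

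**Conclusion.** The concern holds as a matter of identifiability: in one group, the baseline-TIR-by-intervention term cannot be read as effect modification. Under before/after coding with baseline in the outcome, regression to the mean alone gives p<0.10 in roughly 20–90% of studies (21% at rho 0.95, 89% at rho 0.5) against a nominal 10%. The 12-month change regression gives 17–76%. The direction of the bias is certain and its size is not, because rho is assumed and the coding is undefined. The figures also assume normal data, equal SDs and complete visits. The mechanism is noise in the baseline TIR window, not the A1c entry criterion. The age interaction does not share it, since age is not a component of the change. The plan should be changed, but the primary feasibility and acceptability conclusions are unaffected.

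**What to change.** In the Protocol Summary, Section 6.4 and Section 8.4, delete baseline TIR from the p<0.10 effect-modification screen and keep it only as a covariate for post-baseline outcomes. Define how the intervention is coded for any interaction that remains.

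If dependence on starting level is of interest, report it descriptively with a confidence interval, and state that it cannot be separated from regression to the mean without a control group.

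Oldham / Pitman-Morgan may be shown only as a sensitivity analysis, using equal-length CGM windows at baseline and month 12. The text should state that it tests equality of the two variances and therefore also flags when individual response varies independently of baseline.

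The cost is wording in three places and the loss of one exploratory claim. Data collection and visits do not change, and the 12-month versus baseline comparison in Hypothesis 2b stays.
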